Official Title: Evaluating the Effectiveness of a Food is Medicine Community Health Worker Program for Pregnant Women: Addressing Social Needs and Improving Health Outcomes

NCT#: NCT06180811

Document Date: December 29, 2023

Statistical Analysis Plan

Aim 1: To assess the feasibility of the Women's Health Delaware Food Farmacy and refine the program as needed

Descriptive statistics will be used to summarize the feasibility (i.e., acceptability, demand, and implementation; Bowen et al., 2009) of the Women's Health Delaware Food Farmacy. The feasibility will be assessed using metrics such as: (1) program satisfaction; (2) study recruitment, enrollment, and retention; (3) meals provided; (4) food consumption; (5) Community Health Worker interactions; and (6) educational videos watched. In addition, open-ended questions related to program satisfaction will be analyzed using thematic analysis.

Aim 2: To determine the prevalence of and change in social needs

Descriptive statistics will be run to summarize the number of social needs identified at baseline and postpartum and the social needs resolved and unresolved through resource referrals among patients in both the Women's Health Delaware Food Farmacy and the usual standard of care. Social needs will be identified by administering ChristianaCare's Social Determinants of Health Screener (adapted from the Accountable Health Communities Health-Related Social Needs Screening Tool; the Protocol for Responding to & Assessing Patients' Assets, Risks & Experiences Screening Tool; and the Health Leads Social Needs Screening Toolkit) and sending resource referrals on patients' behalf to support their needs, both of which are standard of care. General/generalized linear models will be run to compare changes in social needs at baseline to postpartum among all participants.

Aim 3: To evaluate the effectiveness of the Women's Health Delaware Food Farmacy on maternal and child health, healthcare utilization, and clinical event outcomes as well as patient-reported outcomes compared to the usual standard of care

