A series of general/generalized linear models will be run to compare patients in the Women's Health Delaware Food Farmacy compared to the usual standard of care on a number of maternal and child health outcomes (e.g., gestational age and preeclampsia), healthcare utilization (e.g., Neonatal Intensive Care Unit admission and maternal length of stay), and clinical events (e.g., cesarean delivery and fetal death) as well as patient-reported outcomes (e.g., food security, dietary intake, quality of life, and cost-related medication underuse). Models will include indicators for randomization blocks and will also control for baseline estimates, when applicable, and relevant covariates will be considered to improve the precision of estimation of effects. In order to adjust for multiple comparisons, the Benjamini-Hochberg procedure will be used for controlling the false discovery rate (Benjamini & Hochberg, 1995). In addition, the intent-to-treat and treatment on the treated impacts will be calculated (Imbens & Angrist, 1994).

References

- Benjamini, Y., & Hochberg, Y. (1995). Controlling the false discovery rate: A practical and powerful approach to multiple testing. *Journal of the Royal Statistical Society: Series B* (*Methodological*), 57(1), 289–300. https://doi.org/10.1111/j.2517-6161.1995.tb02031.x
- Bowen, D. J., Kreuter, M., Spring, B., Cofta-Woerpel, L., Linnan, L., Weiner, D., Bakken, S., Kaplan, C. P., Squiers, L., Fabrizio, C., & Fernandez, M. (2009). How we design feasibility studies. *American Journal of Preventive Medicine*, *36*(5), 452–457. https://doi.org/10.1016/j.amepre.2009.02.002
- Imbens, G. W., & Angrist, J. D. (1994). Identification and estimation of local average treatment effects. *Econometrica*, 62(2), 467–475. https://doi.org/10.2307/2951620

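### Does leaving the Benjamini-Hochberg level and family unstated make the Aim 3 multiplicity rule faulty?

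*SAP*

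**What the plan says.** The Aim 3 heading in the SAP covers "maternal and child health, healthcare utilization, and clinical event outcomes as well as patient-reported outcomes compared to the usual standard of care". The paragraph beneath it opens with "A series of general/generalized linear models will be run to compare patients" and then gives example outcomes in four groups:

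- maternal and child health: gestational age, preeclampsia;
- utilization: Neonatal Intensive Care Unit admission, maternal length of stay;
- clinical events: cesarean delivery, fetal death;
- patient-reported: "food security, dietary intake, quality of life, and cost-related medication underuse".

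One sentence on multiplicity follows, for all of them: "In order to adjust for multiple comparisons, the Benjamini-Hochberg procedure will be used for controlling the false discovery rate". The SAP gives no value of q, no significance level and no definition of the family. It does not mention separate adjustment by group.

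**The concern.** Benjamini-Hochberg (BH) turns p-values into claims only once q and the number of tests in the family are set. With both open, the SAP could be read as one family for the whole series, as two (clinical and utilization outcomes apart from patient-reported ones), or as four (one per group in the list). A complete outcome list in the protocol would not by itself settle the grouping.

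Two things would be at stake. If the grouping were chosen after the p-values were known, it could be chosen to favor a wanted claim. And a reader of a claim about preeclampsia or neonatal intensive care would not know which error rate it carried.

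**Working it through.** **Inputs.** The SAP states no sample size, power, significance level or q, so there is no figure of its own to reproduce. Assumptions: q = 0.05, with 0.10 as the range; two-sided tests; the ten example outcomes, 2 + 2 + 2 + 4, of which 6 are clinical or utilization and 4 patient-reported. The lists are examples only, so ten is not the trial's real count.

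**Rule.** With m tests, reject the k smallest p-values, where k is the largest i with p(i) ≤ q·i/m.

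**Lowest cut-off for a clinical outcome, q/m.**

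| | One family (10) | Two (6+4) | Four (2+2+2+4) |
|---|---|---|---|
| q = 0.05 | 0.05/10 = 0.005 | 0.05/6 = 0.0083 | 0.05/2 = 0.025 |
| q = 0.10 | 0.010 | 0.0167 | 0.050 |

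These are only the bottom rungs. BH is a step-up rule, so a p-value above q/m can still be rejected when others in its family are small.

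**Overall false discovery rate with every outcome null.** For k families of independent tests, each at level q, this is 1 − (1 − q)^k.

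| | k = 1 | k = 2 | k = 4 |
|---|---|---|---|
| q = 0.05 | 5% | 1 − 0.95² = 9.75% | 1 − 0.95⁴ = 18.5% |
| q = 0.10 | 10% | 1 − 0.90² = 19% | 1 − 0.90⁴ = 34.4% |

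Within each family the rate stays at q. Only the coverage of the guarantee changes.

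**One invented set of p-values.** Food security 0.004, diet 0.012, gestational age 0.021, neonatal intensive care 0.045, length of stay 0.048, quality of life 0.09, medication underuse 0.20, preeclampsia 0.30, cesarean 0.40, fetal death 0.80.

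- q = 0.05, one family: food security passes (0.004 ≤ 0.005), and no later p-value meets its rung. One claim, none clinical.
- q = 0.05, two families: diet is added (0.012 ≤ 2 × 0.05/4 = 0.025). Two claims, none clinical.
- q = 0.05, four families: gestational age (0.021 ≤ 0.025) and both utilization outcomes (0.048 ≤ 0.05) are added. Five claims.
- q = 0.10: the same five claims under all three groupings.

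So the readings can differ but need not. The one- and two-family readings agree on clinical claims at both levels here.

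**How often they differ.** One million simulated sets of ten independent z-tests per scenario, q = 0.05. True clinical effects have 80% single-test power (mean z of 2.80) and lie in different groups; near-certain effects have mean z of 5.

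| Scenario | One and two families differ on clinical claims | Clinical power, one / two families |
|---|---|---|
| All null | 2.1% | – |
| Two clinical effects only | 15.3% | 55.9% / 63.2% |
| Two clinical, two near-certain patient-reported | 8.8% | 67.5% / 63.3% |

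Adding the four-family reading raises disagreement to 11.5%, 33.7% and 20%. At a correlation of 0.3 between tests, those three figures are 10.6%, 33.9% and 20.8%.

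**False clinical claims when no clinical outcome is affected.** Under two families the chance of at least one is 5.0%. Under one family it is 3.1% with no patient-reported effect, 8.8% with two near-certain ones and 14.1% with four. The last follows by hand: after four sure rejections the next rung is 5 × 0.05/10 = 0.025, and 1 − 0.975⁶ = 14.1%.

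**The case for a change.** The strongest case for acting is that a procedure named without its level and family is not yet a rule, that two sentences would complete it, and that no reading is safely conservative. A food program might well move food security and diet without moving clinical outcomes. Pooling then lets strong patient-reported results loosen the clinical cut-off.

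Part of this stands. The SAP does omit q and the family, and the groupings can give different claims. The rest is weaker:

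- **The readings do not have equal support.** One series of models and one adjustment sentence point to one family. The two-family reading rests on how a list is joined, and the four-family reading only on its labels. The four-family reading produces the largest disagreement figures.
- **The cut-off range is inflated.** Going from 0.005 to 0.050 is tenfold only by combining a fivefold effect of the least-supported grouping with a doubling of an assumed q, and by treating the bottom rung as the effective cut-off.
- **The 8.8% and 14.1% figures do not measure vagueness.** They are family-wise probabilities, whereas the plan chose false discovery rate control. They would remain if a single family at q = 0.05 were written out in full.
- **Choosing the family after seeing results is conjecture.** Nothing in the document suggests it. A level and an outcome hierarchy are also often set in the protocol, which is not shown.
- **The missing q matters less than the missing family.** BH-adjusted p-values can be reported without q and read against any level.

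**Conclusion.** The omission is real, but no change to the plan follows. An analyst following the SAP would pool the Aim 3 tests, apply BH at a conventional level and obtain a valid result, and nothing in the plan leads to a wrong one. Writing down q and the family would record that reading without replacing it with a better method.

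Choosing two families instead is a trade-off. It gains about 7 points of clinical power when only clinical outcomes respond (63.2 − 55.9 = 7.3) and loses about 4 when patient-reported outcomes respond too (67.5 − 63.3 = 4.2). It also raises the overall false discovery rate with every outcome null from 5% to 9.75% (from 10% to 19% at q = 0.10).

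The size of the issue is the disagreement on clinical claims between those two readings: about 2%, 15% and 9% of simulated trials in the three scenarios. These figures rest on q = 0.05, the ten example outcomes split 6 and 4, independent two-sided tests and the assumed effect sizes. Other counts or levels would move the percentages, but not the conclusion that the false discovery rate is controlled within the family under either reading.

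### Does the Aim 3 plan leave open whether its multiplicity-adjusted models are intent-to-treat, and how the effect in treated women is estimated?

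*SAP*

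**What the plan says.** The Aim 3 paragraph of the SAP runs in four steps.

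1. A series of general or generalized linear models "will be run to compare patients in the Women's Health Delaware Food Farmacy compared to the usual standard of care" on maternal, child, utilisation, clinical-event and patient-reported outcomes.
2. The model terms: "Models will include indicators for randomization blocks and will also control for baseline estimates, when applicable".
3. Multiplicity: "In order to adjust for multiple comparisons, the Benjamini-Hochberg procedure will be used for controlling the false discovery rate".
4. The last sentence: "In addition, the intent-to-treat and treatment on the treated impacts will be calculated". It carries a citation whose title in the reference list is "Identification and estimation of local average treatment effects".

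The paragraph does not rank the two impacts or say whether both enter the false-discovery family. It does not define a treated woman or give a scale for the treated effect on binary outcomes. Under Aim 1 the SAP lists several measures of programme delivery and use (meals, food eaten, Community Health Worker contacts, videos), but only as feasibility metrics.

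**The concern.** The order of the sentences invites a literal reading: the models and their adjusted p-values come first, and intent-to-treat is then added. No sentence says that a woman assigned to the programme who takes up none of it stays in that arm of the adjusted models. If the models grouped women by receipt, differences between women who do and do not take up the programme would be read as programme effect, and that reading would carry the adjusted p-value.

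The treated effect raises a second worry. With several measures of receipt on file, the choice of who counts as treated could be made after outcomes are known. For binary outcomes such as preeclampsia or cesarean delivery, rescaling an odds ratio by uptake does not give the odds ratio among women who comply.

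**Working it through.** The SAP gives no sample size, uptake, risk or false-discovery level, so there is no figure to reproduce. Every number below is an assumption used for illustration.

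**1. The text.**
- Aim 3 describes one set of models. Intent-to-treat impacts have no other source in the document, so the literal reading needs a third, by-receipt analysis that no sentence plans.
- "Models will include indicators for randomization blocks" fits a comparison of arms as randomised.
- Describing women as patients in the programme is the SAP's label for an arm. Aim 2 uses the same construction for both the programme and usual care, so it does not signal receipt.

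**2. What a by-receipt model would do.** Let c be uptake, and rc and rn the outcome risks in takers and non-takers, with no true effect. Usual-care risk is c·rc + (1−c)·rn, so receivers against all usual care differ by −(1−c)(rn − rc). With rc = 0.30, rn = 0.50 and c = 0.7, usual-care risk is 0.21 + 0.15 = 0.36 and the bias is 0.30 − 0.36 = −0.06. With 200 per arm:

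- SE = √(0.30×0.70/140 + 0.36×0.64/200) = √(0.001500 + 0.001152) = 0.0515
- Bias/SE = −1.17, and the nominal 5% two-sided error becomes about 21%.

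At 90% and 80% uptake the biases are −0.02 and −0.04, and the error is about 7% and 13%. The bias is zero if rn = rc, and +0.03 at 70% uptake if rn = 0.20. These figures show why as-randomised grouping matters. They describe an analysis the SAP does not propose.

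**3. What the plan gives when followed.** Suppose usual-care risk is 0.20 in takers and 0.30 in non-takers, the true difference in takers is −0.06, and no usual-care woman receives the programme. At 70% uptake:

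- Usual care: 0.7×0.20 + 0.3×0.30 = 0.23
- Programme arm: 0.7×0.14 + 0.3×0.30 = 0.188
- Intent-to-treat: 0.188 − 0.23 = −0.042
- Treated effect (ratio): −0.042/0.7 = −0.06, the true value

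At 90%, 50% and 30% uptake the ratio is again −0.06.

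**4. Does it matter which impact carries the adjusted p-value?** Let U be the difference in uptake between arms. Under no effect, to first order, SE(ITT/U) = SE(ITT)/U, so (ITT/U)/(SE(ITT)/U) = ITT/SE(ITT). The two tests are essentially the same. If both p-values enter the Benjamini-Hochberg family, m outcomes become 2m entries in equal pairs. The outcome ranked k then holds ranks 2k−1 and 2k, and its larger threshold is 2kq/(2m) = kq/m, the same as with m entries. Whether the treated estimate is inside or outside the family would seldom change a finding.

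**5. What remains open for the treated estimate.**
- *Share treated.* With the intent-to-treat difference fixed at −0.03, the ratio is −0.033, −0.043, −0.060 or −0.100 when 90%, 70%, 50% or 30% count as treated.
- *Cut-off.* Suppose 90% receive something, 60% reach a cut-off, and partial receipt has a fraction d of the full effect. The ratio is then (0.6 + 0.3d)/0.6 times the effect in women reaching the cut-off: 1.00, 1.125 or 1.25 for d = 0, 0.25 or 0.5.
- *Scale.* Suppose takers' risk falls from 0.30 to 0.15 (odds ratio 0.41) at 70% uptake. Dividing the intent-to-treat log odds ratio by 0.7 gives an odds ratio of 0.34 if non-takers' risk is 0.05 and 0.49 if it is 0.50. The risk-difference ratio returns −0.15 in both.

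The SAP sets no cut-off and does not call for odds-ratio rescaling, so these are possible later choices, not faults in a stated rule.

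**The case for a change.** The strongest case for a change is that block terms can also sit in a by-receipt model and so do not define who is analysed in which arm. The SAP itself brings up intent-to-treat, the treated effect and multiplicity. How the three relate is SAP content, and one sentence would settle it cheaply. The citation suggests a method but does not choose the receipt variable or the scale, and step 5 shows that the choice of who is treated can triple the reported effect.

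Part of this stands. The two impacts are not ranked, and the size of the treated estimate depends on choices the SAP leaves open. A local average effect also equals the effect on the treated only if no usual-care woman receives the programme.

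The rest is weaker. An analyst working from a randomised design, block terms and a named intent-to-treat impact would have no reason to fit by-receipt models as the main analysis. The definition of receipt depends on the description of the intervention, which the protocol, not available for this review, may well contain. To fix it here as any contact at all, or to move the treated estimate outside the false-discovery family, would be a matter of preference and not the correction of an error.

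**Conclusion.** No change follows. The most natural reading of Aim 3 is that the adjusted models compare women as randomised and supply the intent-to-treat impacts, with the treated effect obtained from them by the instrumental-variable approach that the citation indicates. On that reading the intent-to-treat result is unaffected, and the treated effect adds essentially no separate test.

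What is missing is detail on a companion estimate: who counts as treated, and the scale for binary outcomes. On the assumed figures this moves its size from −0.033 to −0.100, but not its sign or its test. Analysts can settle these points sensibly when they specify that estimate.

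The conclusion assumes that no by-receipt main analysis is intended, which nothing in the SAP suggests, and that the treated effect uses randomised arm as the instrument. The error rates of 7% to 21% apply only if the first assumption fails.
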